### 2.4.4.1 Analysis of primary efficacy endpoint(s)

The primary efficacy endpoint will be analyzed on the mITT population. In the primary analysis, assessments at week 52 will be used regardless of whether the patient has previously discontinued treatment.

Due to the non-normality of the endpoint distribution, the absolute change from baseline in % predicted FVC at week 52 as defined in [Section 2.1.3.1](#) will be analyzed in the mITT population using a rank ANCOVA model adjusted on the stratification factor (with/without background therapy). This model will use the ranks of absolute change from baseline to week 52 in % predicted FVC as the outcome and the ranks of baseline % predicted FVC as a covariate. In case of ties, the mean of the corresponding ranks will be assigned.

To summarize, the following steps will be performed:

A) On the pool of arms SAR156597 200mg qw and placebo:

1. Imputation of missing data at 52 weeks

a) Week 52 missing values due to reasons other than death or lung transplant

- i. Patients in active arm and taking treatment at 52 weeks: Missing values at 52 weeks will be imputed using a model estimated from the subset of patients in the active arm who completed the 52-week treatment period and with a week 52 value. The imputation model will be based on a Mixed Model with Repeated Measures (MMRM) with fixed categorical effect of stratification factor (with/without Background Therapy) and repeated categorical effect for time point (baseline, week 12, week 24, week 36, week 52). Parameters will be estimated with the Newton-Raphson algorithm, an unstructured covariance matrix will model the within-patient errors, and the denominator degrees of freedom will be estimated using Satterthwaite's approximation. Missing values at 52 weeks will be imputed using the empirical best linear unbiased prediction (EBLUP).
- ii. Other patients (patients in active arm and not taking treatment at 52 weeks; or patients in placebo arm): Missing values at 52 weeks will be imputed using a model estimated from the subset of patients in the placebo arm who completed the 52-week treatment period and with a week 52 value. The imputation model will be based on a Mixed Model with Repeated Measures (MMRM) with fixed categorical effect of stratification factor (with/without Background Therapy) and repeated categorical effect for time point (baseline, week 12, week 24, week 36, week 52). Parameters will be estimated with the Newton-Raphson algorithm, an unstructured covariance matrix will model the within-patient errors, and the denominator degrees of freedom will be estimated using

- Satterthwaite's approximation. Missing values at 52 weeks will be imputed using the empirical best linear unbiased prediction (EBLUP).
- iii. When running the imputation model, if the predicted absolute change from baseline calculated from the predicted week 52 value is greater than zero (increases above baseline), it will be set to zero.
  - iv. The non-monotone missing patterns with a week 52 value available will not be imputed.
- b) Week 52 missing values due to lung transplant:
    - i. Any % predicted FVC value assessed after a lung transplant will be considered as missing.
    - ii. No imputation of a week 52 value for % predicted FVC. In step 2, patients will be ranked worse than missing data due to reasons other than death or lung transplant.
  - c) Week 52 missing values due to death :
    - i. No imputation of a week 52 value for % predicted FVC. In step 2, patients will be ranked worse than missing data due to lung transplant.
2. Rank ANCOVA
- a) Ranking within each stratum of the stratification factor (with/without Background Therapy)
    - i. Death: Missing data due to death will be ranked based on a time-to-death, with shortest time until death as the worst (lowest) rank (from 1 to  $n_{\text{stratum,death}}$ ).
    - ii. Lung transplant: Missing data due to lung transplant will be ranked based on a time-to-lung transplant, with shortest time until lung transplant as the worst (lowest) rank (from  $n_{\text{stratum,death}}+1$  to  $n_{\text{stratum,death}}+n_{\text{stratum,lungtransplant}}$ ). So, missing data due to lung transplant will be less penalized than deaths.
    - iii. Other: Absolute change from baseline at 52 weeks in % predicted FVC values will be calculated from observed and imputed week 52 % predicted FVC values and then ranked (from  $n_{\text{stratum,death}}+n_{\text{stratum,lungtransplant}} + 1$  to  $n_{\text{stratum}}$ ).
    - iv. Standardization of ranks using the NPLUS1 option of PROC RANK on SAS with the by statement for the stratification factor (with/without Background Therapy).
  - b) Adjustment on baseline % predicted FVC covariate
    - i. The residuals from the linear regression of response ranks on baseline ranks will be calculated within each stratum of the stratification factor (with/without Background Therapy) using the following PROC GLM on SAS:

```
proc GLM data=xx;  
by stratification_factor;  
model chg_Rank=base_Rank;  
output out=residual r=resid;  
run;
```

- c) Test of treatment effect using the CMH2 option of PROC FREQ on SAS and the residuals as scores
  - i. The qw arm will be compared to placebo using a Mantel-Haenszel mean score chi-square test at a two-sided type-I error level of 5%. This test will be stratified on the stratification factor.

B) On the pool of arms SAR156597 200mg q2w and placebo:

Same steps as A except for 2c: the q2w arm will be compared to placebo using a Mantel-Haenszel mean score chi-square test at a two-sided type-I error level of 5% only if the qw arm versus placebo comparison was significant. This test will be stratified on the stratification factor.

Descriptive statistics for values and changes from baseline will be presented by treatment arm and background therapy status for each time point. The mean (SD) % predicted FVC values and the mean (SD) absolute change from baseline in % predicted FVC over time will be graphically represented by treatment arm and by background therapy status without any imputation.

A specific table will describe the following items by treatment arm and background therapy:

- The number (%) of patients with an observed week 52 value for % predicted FVC
  - The mean (SD) and median (Q1:Q3) of baseline and week 52 values of % predicted FVC for those patients
  - The mean (SD) and median (Q1:Q3) of absolute change from baseline at 52 weeks in % predicted FVC for those patients
- The number (%) of patients having a missing data due to death at week 52,
- The number (%) of patients having a missing data due to lung transplant at week 52,
- The number (%) of patients having a missing data due to reasons other than death or lung transplant,
- The mean (SD) of baseline % predicted FVC value for all patients included in the analysis
- The p-values versus placebo of rank ANCOVA (only by treatment arm).

The magnitude of treatment effect will be assessed as follows:

- For each quartile of ranks per pool (A then B) of treatment arms, the following items will be displayed:
  - The number (%) of patients with death
  - The number (%) of patients with lung transplant
  - The number (%) of patients with an observed or imputed week 52 value for % predicted FVC
    - The median (Q1:Q3) absolute change from baseline at 52 weeks in % predicted FVC for those patients

This will allow to compare across treatment arms the distribution of deaths, lung transplants and absolute change from baseline at 52 weeks within each quartile (first quartile corresponding to the worst ranks). As ranks will be performed by background therapy status, one table will be provided on patients with background therapy status and another one will be provided on patients without background therapy status.

- The worsening of the change from baseline at 24 weeks and 52 weeks (imputed and observed values) will be described thanks to the number (%) of patients by treatment arm and by background therapy status in following categories:
  - Stability or improvement (decrease  $\leq 0\%$ )
  - Decrease  $>0\%$  to  $\leq 5\%$
  - Decrease  $>5\%$  to  $\leq 10\%$
  - Decrease  $>10\%$  or death or lung transplant

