4 INTRODUCTION AND RATIONALE

4.1 INTRODUCTION

Idiopathic pulmonary fibrosis (IPF) is a progressive, diffuse, and distinct chronic fibrosing interstitial pneumonia of unknown cause that is uniformly fatal with a median survival of approximately 3 years (1). The clinical course of IPF is variable and not predictable; the rate of decline and progression to death may take several clinical forms: slow physiologic deterioration with worsening severity of dyspnea, rapid deterioration, and progression to death, or periods of relative stability interposed with periods of acute respiratory decline sometimes manifested by hospitalizations for respiratory failure (2). Epidemiological data still qualify IPF as a “rare disease”, even though international studies seem to report an increasing incidence, with current estimates between 4.6 and 16.3 per 100 000 person-years and a prevalence of 13 to 20 cases per 100 000 ((3), (4), (5)). There is a higher predominance of the disease in men (1.5 to 1.7:1) than in women and the frequency increases with age (5). The most important environmental risk factors are cigarette smoking, exposure to metal and wood dust(1), and infectious agents including both viruses and bacteria(6). Genetic transmission occurs in about 0.5% to 3.7% of patients with IPF (7). The diagnosis of IPF often requires a multidisciplinary approach, involving pulmonologists, radiologists, and pathologists experienced in the field of interstitial lung diseases(8). The pathogenic mechanisms are unclear, but a growing body of evidence indicates that the disease is the result of an abnormal behavior of the alveolar epithelial cells that provoke the migration, proliferation, and activation of mesenchymal cells, with the formation of fibroblast and myofibroblast foci. Activated myofibroblasts secrete exaggerated amounts of extracellular matrix molecules with the subsequent destruction of the lung architecture (9). Pirfenidone (Esbriet®, Roche), an oral drug that is hypothesized to inhibit the synthesis of transforming growth factor-beta, was approved so far in Japan, China and in the European Union for the treatment of IPF. Very recently, the FDA approved pirfenidone as well as nintedanib (Ofev®), an oral kinase inhibitor for the treatment of IPF. Per labeling information, these two drugs were shown to significantly reduce the decline of lung function as compared to placebo. No statistically significant effect on death was demonstrated. Lung transplantation is the only therapy that prolongs survival in advanced IPF, although the post-transplantation 5-year survival for patients with IPF is about 48% (10). Interleukin 4 (IL)-4 and interleukin 13 (IL-13) are structurally related cytokines expressed by T helper type 2 lymphocytes and are ligands that share in common at least 1 receptor subunit (IL-4R alpha) (11), (12). Elevations in IL-4 and IL-13 and their receptors have been linked to the pathogenesis of IPF (13), (14). In IPF patients, IL-13 and IL-4 levels in bronchial alveolar lavage fluid are elevated compared to normal controls (15). Such evidence suggests that therapies capable of suppressing or neutralizing these cytokines have the potential for delaying the progression of fibrosis in IPF patients. SAR156597 is an engineered humanized bispecific IgG4 antibody that binds and neutralizes both IL-4 and IL-13. It utilizes an innovative tetravalent bispecific tandem immunoglobulin format to combine the antigen binding domains of an anti-IL-4 antibody and an anti-IL-13 antibody into a single molecule. SAR156597 shows high affinity for IL-4 and IL-13 from both humans and cynomolgus monkeys, and each antibody has binding sites for 2 IL-4 and 2 IL-13 cytokines.

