### **1.3 DETERMINATION OF SAMPLE SIZE**

Approximately 300 patients will be randomized in this study, 100 per treatment arm. Based on the enrollment in prior studies of this population approximately half of the patients are expected to be older than 65.

The sample size calculations are based on the primary efficacy variable of % predicted FVC change from baseline to week 52, with the following assumptions:

- A common standard deviation of 12% is assumed based on the data from previous trials (26)
- A 5% mean difference between each dose and placebo in change from baseline in % predicted FVC
- A 2-sided 5% significance level with 80% power

Ninety two (92) patients per treatment arm will yield 80% power to detect a 5 percentage point difference between the treatment groups and placebo. Additional patients will be randomized in each regimen to allow for dropouts; therefore, approximately 100 patients will be randomized into each treatment arm, for a total sample size of approximately 300 patients for the study.

[figure not shown]
As a rank-based method will be used for analysis the actual power may differ from these calculations, however, calculations based on the ASCEND study (28), which used the same analysis method and endpoint confirm that the planned analysis should have at least 80% power. No adjustment is made for multiplicity since a hierarchical testing procedure is proposed.

Calculations were made using nQuery Advisor 7.0.

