**Table 4 - primary efficacy outcome algorithm in case of missing data**

Type of missing data	Sensitivity 1	Sensitivity 2
Missing data at week 52 due to reasons other than death or lung transplant	Multiple imputation of week 52 value using copy increment from reference (CIR) approach (assuming normality)	No imputation
Missing data at week 52 due to death	Multiple imputation of week 52 value using the distribution of the last available % Predicted FVC assessment of dead and lung transplanted patients	No imputation
Missing data at week 52 due to lung transplant	Multiple imputation of week 52 value using the distribution of the last available % Predicted FVC assessment of dead and lung transplanted patients	No imputation

**Sensitivity analysis 1:** Assessments at week 52 will be used regardless of whether the patient has previously discontinued treatment.

The absolute change from baseline to week 52 in %predicted FVC will be analyzed on the mITT population using a Mixed Model with Repeated Measures (MMRM) with the fixed categorical effects of treatment arm, stratification factor (with/without Background Therapy), time point, treatment-by-time point interaction, stratification factor-by-treatment-by-time point interaction, as well as the continuous fixed covariate of % predicted FVC baseline. Parameters will be estimated with the Newton-Raphson algorithm, an unstructured covariance matrix will model the within-patient errors, and the denominator degrees of freedom will be estimated using Satterthwaite's approximation.

As for primary analysis, the non-monotone missing patterns with a week 52 value available will not be imputed.

Week 52 missing values (due to reasons other than death or lung transplant) will be imputed using the CIR multiple imputation approach (3). The CIR approach is a multiple imputation methodology based on a Gaussian repeated-measures model:

- First, a large number of datasets will be imputed using the posterior distribution of a linear model containing:
  - baseline value,
  - week 12, week 24 and week 36 time points values (if occurred before the current time point to be imputed),
  - stratification factor,
  - treatment arm\* time point interaction,
  - treatment arm.

This requires a monotone missingness, which is why all time points will be imputed sequentially to determine week 52 value.

- Then, the analysis will be run independently on those imputed datasets to estimate parameters.

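### The imputation model for the primary endpoint has no fixed effect for time, so read literally it imputes early losses too favourably

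*SAP*

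**What the plan says.** For living, non-transplanted patients with no Week 52 value, SAP 2.4.4.1 imputes from one of two models. Step A.1.a(i) covers active patients still on treatment at Week 52 and uses active-arm completers. Step A.1.a(ii) covers everyone else and uses placebo completers. Both are specified as an MMRM "with fixed categorical effect of stratification factor (with/without Background Therapy) and repeated categorical effect for time point". The time points are baseline and Weeks 12, 24, 36 and 52, the covariance is unstructured, and the imputed value is the EBLUP. A predicted change above zero is set to zero.

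The MMRM in sensitivity analysis 1 is written differently: "with the fixed categorical effects of treatment arm, stratification factor (with/without Background Therapy), time point, treatment-by-time point interaction". Sensitivity analysis 2 and the 6-MWT, SGRQ, EQ-5D-5L and DLCO models likewise name time point among the fixed effects.

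SAP Table 1 (section 1.5) and SAP Appendix B describe the same imputation as a linear regression on completers. The SAP gives code for the rank-regression step but none for the imputation.

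**The concern.** In an MMRM the repeated effect indexes the covariance matrix; it does not put a visit term in the mean. The SAP keeps fixed and repeated effects apart everywhere else, so a programmer following steps (i) and (ii) would fit one constant mean per stratum across all five visits, including baseline. The model's mean change from baseline to Week 52 is then zero, although Protocol 4.2.2 justifies the 52-week duration by the decline expected over 12 months.

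The imputed values enter the ranks of the primary test. That test gates the q2w comparison and the disease-progression test (SAP 2.4.4.3). The error is largest for patients with few visits, so the arm that loses more patients early would gain. A second programmer, following the linear-regression wording in Table 1, would fit an intercept, carry the decline, and could report a different primary p-value.

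**Working it through.** **The plan's own figure.** SAP 1.3 uses a difference of 5, SD 12, two-sided 5% and 80% power. The normal approximation gives n = 2(1.960 + 0.842)² × (12/5)² = 90.4, so 91. The noncentral t gives power 0.798 at 91 and 0.803 at 92. This reproduces "Ninety two (92) patients per treatment arm will yield 80% power to detect a 5 percentage point difference". Going from 92 to 100 implies a loss of 1 − 92/100 = 8%.

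**Inputs.**
- SD of the 52-week change: 12 (SAP 1.3).
- Baseline mean 67.5 and SD 17.4: assumed, backed out of the tercile cuts 60 and 75 in SAP 2.1.1 under normality.
- 52-week decline D: not in the documents; range 5 to 10 points, the same in both strata.
- Measurement-error SD: not in the documents; 3.5 assumed.
- Slope SD: √(12² − 2 × 3.5²) = 10.93 per year.

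**Model.** With t = week/52:
- Visit means: m = 67.5 − D·t.
- Covariance: S_jk = 17.4² + 10.93²·t_j·t_k, plus 3.5² on the diagonal.
- Constant mean forced by the literal model (maximum likelihood): μ = (1′S⁻¹m)/(1′S⁻¹1).
- Fitted covariance: S + dd′, where d = m − μ.
- The EBLUP conditions on the visits observed.

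**Worked case: D = 6, last seen at Week 12.** The true means at baseline, Week 12 and Week 52 are 67.50, 66.12 and 61.50. The fitted constant is μ = 67.09. The EBLUP weights on baseline and Week 12 are −0.460 and 1.474. For an average patient the prediction is 67.09 − 0.460(0.41) + 1.474(−0.97) = 65.47, a change of −2.03. The truth is −6, so the imputation is 3.97 points too favourable. With time point in the mean, the average prediction is −6.00.

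**Zero cap.** Across patients the predicted change is normal with mean a and SD b. The capped mean is aΦ(−a/b) − bφ(a/b).
- Literal model: a = −2.03, b = 8.16 gives −4.37, an error of +1.63.
- With time: a = −6.00, b = 7.17 gives −6.81, an error of −0.81.

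**All cases** (error in points; positive is too favourable; each cell is last seen Week 12 / 24 / 36):

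| Decline | As written, before cap | As written, after cap | With time, after cap |
|---|---|---|---|
| 5 | +3.36 / +1.70 / +0.79 | +0.97 / −0.93 / −1.81 | −1.03 / −1.86 / −2.23 |
| 6 | +3.97 / +1.96 / +0.89 | +1.63 / −0.48 / −1.45 | −0.81 / −1.57 / −1.92 |
| 7.5 | +4.80 / +2.28 / +1.02 | +2.52 / +0.10 / −0.97 | −0.55 / −1.21 / −1.53 |
| 10 | +5.99 / +2.64 / +1.13 | +3.81 / +0.87 / −0.34 | −0.27 / −0.75 / −1.01 |

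With time in the mean, the pre-cap error is zero in every cell. The share of Week 12 losses capped at no decline is 34% to 42% as written and 8% to 24% with time. The size depends on the error SD: the same formulas give post-cap Week 12 errors of 0.6 to 3.2 at error SD 3, and 1.7 to 5.1 at error SD 5.

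**Effect on the test** (simulated: SAP cap and stratified rank ANCOVA, 800 runs per scenario, error SD 3).
- 8% missing in each arm, true effect 5: power 76% to 80% under both models.
- No effect, 8% missing on placebo and 25% on active: two-sided rejection 4% to 6% under both models. As written, the mean z is 0.14 to 0.24 towards the drug at declines of 7.5 and 10, about 0.4 if the SD of change is 8, and about zero at a decline of 5.

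A rough check on the scale of means: suppose the 17-point excess in loss all came after Week 12 with the largest error in the table. The shift is 0.17 × 3.81 = 0.65 points against a standard error of 12√(2/100) = 1.70, or 0.38 in z.

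**The case against.** **The wording may be loose shorthand.** The author may have meant a visit effect in the mean, and the linear-regression descriptions point that way. This stands as a doubt about intent. It does not remove the need to correct the text, because the detailed specification is what a programmer would follow.

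**The design limits the damage.** Patients who stop treatment are followed to Week 52 (Protocol 4.2.1), and their Week 52 values count regardless of discontinuation. The efficacy window for Week 52 is wide, Days 309 to 406 (SAP Table 6). Sensitivity analyses 1 and 2 do not use this imputation model. All of this stands.

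**After the cap, adding time moves Week 24 and Week 36 predictions further from the truth in most of these scenarios.** This is also correct. That error comes from the cap, which the plan chose deliberately and which leans against the patient. One misspecification offsetting part of another is not a reason to keep it.

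**Stronger readings to avoid.** A reader might infer that every surviving patient with missing data is imputed far too favourably. The documents do not support that. Transplanted patients are ranked rather than imputed, a baseline and at least one post-baseline value are needed (SAP Table 1), the EBLUP uses each patient's own visits, and the cap pulls predictions down at every visit.

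A reader might also infer a materially inflated type I error. One-sided false-positive rates of 6.6% to 7.7% (nominal 2.5%) can be simulated, but they need an SD of change of 9.4 (slope SD 8, error SD 3.5: √(64 + 24.5)) and 30% against 10% early loss. The plan states SD 12, and nothing in it suggests such losses. At SD 12 and a decline of 6, the 30% against 10% split gives 4.6% if all loss follows Week 12, and 2.8% if it is spread over Weeks 12, 24 and 36.

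Finally, a stratum-by-time term might seem required because "these two drugs were shown to significantly reduce the decline of lung function as compared to placebo". The protocol gives no size for that effect, and ranking and testing are done within stratum, so similar losses put the misfit on both arms. The term is sensible but optional.

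**Conclusion.** The point holds as an error of specification with a modest effect. As written, the imputation model has a constant mean over time, and patients last seen early are predicted too favourably. For Week 12 losses the error is about 3.4 to 6.0 points before the cap and about 1.0 to 3.8 after it. After the cap, Week 24 and Week 36 losses run from about 0.9 too favourable to 1.8 too unfavourable. These are errors per imputed patient, not in the treatment difference.

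At about 8% loss per arm the effect on the primary test is negligible. The direction becomes unsafe only if one arm loses clearly more patients early. The sizes rest on an assumed decline of 5 to 10 points, linear trajectories, error SD 3.5 and dropout unrelated to outcome. They also use maximum likelihood in place of REML and leave out deaths and transplants. Only the SD of 12 comes from the plan. The conflict between the MMRM and linear-regression descriptions needs no assumption.

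**What to change.** In SAP 2.4.4.1, steps A.1.a(i) and (ii), list stratification factor and time point as fixed effects, and keep the unstructured covariance across the five time points and the EBLUP. Add stratum-by-time point if wanted. Replace the linear-regression wording in SAP Table 1 and Appendix B with the same description, and give the model code alongside the code already shown for the rank step. The cost is one line in each step, one MODEL statement and two matching edits, made before unblinding. No new data are needed.

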# 1 OVERVIEW AND INVESTIGATIONAL PLAN

## 1.1 STUDY DESIGN AND RANDOMIZATION

This is a phase 2, proof-of-concept, multicenter, multinational, randomized, placebo-controlled, double-blind, 3-parallel-arm (placebo qw, SAR156597 200mg qw and SAR156597 200mg q2w alternating with placebo every other week), stratified study design.

After a screening phase of up to 4 weeks, patients will be centrally randomized (using allocation from block randomization schedule with stratifying factors) via IRT in a 1:1:1 ratio to 1 of the 3 treatment groups and treated double-blind for approximately 1 year.

Randomization will be stratified according to background therapy in authorized countries at the moment of randomization (patient with background therapy with either pirfenidone or nintedanib versus patient without background therapy). According to protocol amendment No. 10, it is planned to include a maximum of 66% of patient with background therapy.

Only patients with adjudicated IPF status were allowed to be enrolled in the study.

Approximately 300 patients (100 patients per treatment arm) will be recruited and randomized from 109 initiated sites.

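### The SAP's first magnitude display compares arms on median change inside quartiles of the pooled outcome ranks, which cannot measure effect size, and the primary ranking has no between-arm estimate with a confidence interval

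*SAP*

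**What the plan says.** SAP 2.4.4.1 tests each active arm against placebo with a stratified rank ANCOVA. Ranks are computed within background-therapy stratum over one active arm plus placebo (pool A: qw; pool B: q2w). Deaths rank worst, then transplants, then observed or imputed Week 52 changes. The planned output of this test is a p-value.

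For magnitude, the section then lists two displays.

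- The first is a table, one per stratum: "For each quartile of ranks per pool (A then B) of treatment arms, the following items will be displayed". The items are numbers (%) with death, with transplant and with a Week 52 value, and the median (Q1:Q3) change among those with a value. Its stated use is to "compare across treatment arms the distribution of deaths, lung transplants and absolute change from baseline at 52 weeks within each quartile".
- The second gives the numbers (%) in four categories of decline at Weeks 24 and 52, by arm and stratum. Deaths and transplants go in the worst category.

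Other planned outputs bear on effect size:

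- by-arm mean and median (Q1:Q3) change for observed Week 52 values (2.4.4.1);
- cumulative distributions of decline without imputation (2.4.4.1, supportive analysis);
- LS-mean differences with 90% and 95% CIs from the two sensitivity MMRMs (2.4.4.1.1);
- a forest plot of LS-mean differences by subgroup (2.4.4.1.2).

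**The concern.** A quartile of the pooled ranking is a slice of the outcome. Comparing the arms on that same outcome within the slice conditions on the result of treatment. A drug that works moves patients from worse slices to better ones; it does little to the typical value within a slice. The treatment effect is therefore in how many patients of each arm fall in each quartile, while the within-quartile medians stay close together whatever the drug does.

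This is the first display that the SAP names for the magnitude of the primary effect, and SAP Table 1 says the Week 52 analysis will inform the decision to move to Phase 3. A team that read the medians as effect sizes would understate the benefit several-fold. Splitting the table by stratum makes each cell small, so individual rows would often appear to favour placebo.

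**Working it through.** **Inputs (SAP 1.3 and 1.1).** Difference 5: "A 5% mean difference between each dose and placebo in change from baseline in % predicted FVC". SD 12. Test and power: "A 2-sided 5% significance level with 80% power". Allocation 1:1:1, hence 1:1 in each pool.

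**The plan's own figure.** n per arm = 2 × ((1.960 + 0.842) × 12/5)² = 90.4, or 91 by the normal approximation. The t-test version gives 91.4, rounded up to 92, with power 0.803 at 92. This reproduces "Ninety two (92) patients per treatment arm will yield 80% power to detect a 5 percentage point difference".

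**Exact within-quartile medians (normal, no deaths).** Location does not matter, so set placebo ~ N(0, 12) and active ~ N(5, 12), the second number being the SD. The pooled quartile cuts c solve ½Φ(c/12) + ½Φ((c−5)/12) = 0.25, 0.50, 0.75, giving c = −5.77, 2.50 and 10.77. For an arm with mean μ and a quartile from a to b:

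- share of the arm = Φ((b−μ)/12) − Φ((a−μ)/12)
- median = μ + 12·Φ⁻¹{[Φ((a−μ)/12) + Φ((b−μ)/12)]/2}

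Worst quartile, placebo: share Φ(−5.77/12) = 0.315, median 12·Φ⁻¹(0.158) = −12.05. Active: share Φ(−10.77/12) = 0.185, median 5 + 12·Φ⁻¹(0.092) = −10.92. The difference is 1.13.

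| Pooled quartile | Placebo share | Active share | Placebo median | Active median | Difference |
|---|---|---|---|---|---|
| 1 (worst) | 31.5% | 18.5% | −12.050 | −10.917 | 1.13 |
| 2 | 26.7% | 23.3% | −1.541 | −1.255 | 0.29 |
| 3 | 23.3% | 26.7% | 6.255 | 6.541 | 0.29 |
| 4 (best) | 18.5% | 31.5% | 15.917 | 17.050 | 1.13 |

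The true difference is 5 at every percentile. The table's medians show 0.29/5 = 6% to 1.13/5 = 23% of it. The missing part is in the share columns.

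**Sensitivity to assumptions that the documents do not give.**

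- Deaths (assumed equal in both arms, ranked worst): 5% gives 0.31 to 1.20; 10% gives 0.32 to 1.21.
- SD from 8 to 15: 0.28 to 1.14.
- Shape: the SAP says the endpoint is non-normal but does not describe it. With 0-10% deaths, t with 3 df gives about −0.35 to 0.53, and a left-skewed gamma about 0.15 to 2.3. All lie far below 5.

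**Stratum sizes.** If the 66% cap on background therapy is reached, the strata hold about 66 and 34 patients per arm. In simulation with a true 5-point benefit and no deaths, the difference in medians had the wrong sign in roughly 30% to 45% of tables in any given quartile.

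**What the other outputs cover.**

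| Output | Deaths and transplants included | Between-arm estimate with CI | On the primary ranking |
|---|---|---|---|
| Counts in the quartile table | yes | no | yes |
| Decline categories | yes | no | no |
| By-arm observed median (Q1:Q3) | counted separately | no | no |
| Cumulative distributions | no imputation | no | no |
| MMRM, sensitivity analysis 1 | imputed by a different rule | yes | no |
| MMRM, sensitivity analysis 2 | no (on-treatment data only) | yes | no |

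No row has all three.

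**The case against.** The strongest reply is that nobody would have to rely on these medians. The counts in the same table carry the shift (31.5/26.7/23.3/18.5% for placebo against the reverse for active). The decline categories do too: with an assumed placebo mean of −10, decline above 10 points is 50% against 34%, and no decline is 20% against 34%. By-arm observed medians and quartiles sit in the same table as the primary p-value, and the MMRM differences have CIs. All of that stands. A reader might infer that the report would show almost no benefit for a working drug; the documents do not support that, since several planned outputs would show the effect. One caveat remains on the counts: the SAP does not say that the percentage uses the arm total as denominator, and the reading depends on it.

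It is also fair that 0.3 to 1.2 is not a fixed property of the table. It rests on normality, which the SAP rejects, and on assumed death rates; the calculation also ignores the cap at zero on imputed changes. The attenuation is structural, but its exact size is not.

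A third reply is that the quartiles might be cut within each arm, which would recover the full shift. The wording, quartiles of ranks per pool of treatment arms, does not fit that reading.

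Last, the table is descriptive: no test or decision rule uses it. That limits the harm, but the SAP still names it as a measure of magnitude.

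**Conclusion.** Wrong as written, and worth correcting. The within-quartile medians in the first magnitude display cannot be read as an effect size. Under the planning difference and SD with normality, a true 5 points appears as 0.3 to 1.1, or 0.3 to 1.2 with an assumed 0-10% deaths; heavier tails or skew change the figures but leave them far below 5. That pooled-quartile medians are pulled together follows from the construction; the particular values rest on these assumptions.

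The finding is limited to those medians and to one gap. The rank ANCOVA, its type I error and the remaining displays are not in question. The gap is that no planned output gives an unconditioned between-arm estimate with a CI on the ranking that the primary test uses, with deaths and transplants included.

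**What to change.** 1. Drop the between-arm comparison of median change within pooled quartiles. Keep the quartile table as counts (deaths, transplants, Week 52 values) per arm and quartile, and state the arm total within stratum as the denominator.
2. For each active arm against placebo, by stratum, report each arm's own 25th, 50th and 75th percentiles of Week 52 change. Use observed and imputed values, with deaths and transplants placed as worst values.
3. Add one stratified estimate with 95% CI on the primary ranking: a win probability, or a Hodges-Lehmann shift with deaths and transplants as worst values. For scale, the planning assumptions without deaths correspond to a win probability of Φ(5/(12√2)) = 0.62.

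The cost is one table shell and a few lines in SAP 2.4.4.1. No new data are needed, and the primary test and its type I error do not change.
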